17 peginterferon alfa when added to long-term nucleoside therapy in patients with chronic HBV
18 infection (both HBeAg-positive and -negative). We hypothesize that the extended pretreatment with
19 NUCs will modify the responsiveness to peginterferon. These effects will be studied by analyzing the
20 expression pattern of ISGs, the response of NK cells prior to and after peginterferon injection
21 resulting in improved transcriptional control of cccDNA, the induction of antibodies against HBe and
22 HBsAg and T cell responses.

23 Primary endpoints of this trial will be the changes in expression levels of ISG's, intrahepatic total HBV
24 DNA and cccDNA content, changes in NK cell effector cell function measured before and following a
25 single dose of peginterferon stratified by treatment response and the rates of HBeAg and HBsAg loss
26 and seroconversion in HBeAg positive patients, HBsAg loss and seroconversion rate in HBeAg
27 negative patients. Secondary endpoints will be the induction of HBV-specific memory T cell
28 responses. A post-hoc analysis will stratify response rates upon available viral genotype data and
29 duration of NUC therapy prior to study enrollment. Other secondary end-points will include changes
30 in quantitative HBeAg and HBsAg levels during therapy and safety of the combination regimen.
31 Serological response rates, qHBsAg kinetics and safety end-points will be compared to historical
32 controls of published multicenter randomized trials comparing the efficacy of peginterferon and
33 NUCs in eAg positive and negative HBV carriers

34

HYPOTHESIS

In patients with chronic hepatitis B infection, under long-term viral suppression maintained by NUCs treatment, peginterferon add-on therapy will result in a greater proportion of subjects achieving serological response compared to before peginterferon was added. We hypothesize that response to treatment will be accompanied by measurable changes in host-response gene transcription profile, immune cell activation and function, and quantitative viral biomarker levels.

SPECIFIC AIMS

1. To assess the changes in ISG profile and NK cell function after a single dose of peginterferon in patients receiving long-term NUCs with maintained viral suppression
2. To determine rates of HBeAg and HBsAg loss with or without seroconversion and induction of HBV-specific memory T cells to peginterferon add-on treatment in eAg positive and negative HBV carriers on long-term NUC treatment.

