- 22 10) Hepatocellular carcinoma (HCC), or the presence of a mass on imaging studies of the liver
- 23 that is suggestive of HCC, or an alpha-fetoprotein level of greater than 500 ng/mL.
- 24 11) eGFR < 50 ml/min, serum creatinine > 1.3 mg/dl or urine protein >1 gram/24-hours
- 25 12) History of hypersensitivity to pegylated interferon-alpha
- 26 13) Platelet count <70 mm³/dL
- 27 14) Hgb <12 g/dL for males and <11 g/dL for females
- 28 15) Active ethanol/drug abuse/psychiatric problems such as major depression, schizophrenia,
- 29 bipolar illness, obsessive-compulsive disorder, severe anxiety, or personality disorder that,
- 30 in the investigator's opinion, might interfere with participation in the study.
- 31 16) History of malignancy or treatment for a malignancy within the past 3 years (except
- 32 adequately treated carcinoma in situ or basal cell carcinoma of the skin).
- 33 17) Any medical condition requiring, or likely to require, chronic systemic administration of
- 34 corticosteroids or other immunosuppressive medications during the course of this study.
- 35 18) History of immune-mediated disease, or cerebrovascular, chronic pulmonary or cardiac
- 36 disease associated with functional limitation, retinopathy, uncontrolled thyroid disease,

- 1 poorly controlled diabetes or uncontrolled seizure disorder, as determined by a study
 2 physician.
- 3 19) Presence of conditions that, in the opinion of the investigators, would not allow the patient
 4 to be followed in the current study for at 1 year.
- 5 20) For subjects who interrupt therapy, documentation of a viral load >1,000 IU/ml while off
 6 therapy.
 7

8 **STUDY DESIGN AND PROCEDURES**

9

10 **Screening**

11 Eligible patients will be seen in the outpatient liver clinic of the NIH Clinical Center. At the screening
 12 visit, potential benefits and risks associated with the study will be explained to the study participants
 13 by an investigator in laymen's language. Written informed consent will be obtained and documented
 14 in the participant's chart. Whenever possible, the informed consent form will be provided to the
 15 potential participants in advance. Only the principal and associate investigators from the Liver
 16 Disease Branch, NIDDK, will be eligible to obtain consent for this study.
 17

18 The following screening procedures will be performed:

- 19 (1) Obtain signed informed consent
- 20 (2) History and physical examination
- 21 (3) Symptom questionnaire

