- 22 (4) Fatigue questionnaire (Promise 7)
- 23 (5) Visual analogue scale
- 24 (6) Routine blood panel: Chemistry 20 (sodium, chloride, potassium, bicarbonate, calcium,
 25 phosphate, magnesium, glucose, blood urine nitrogen, creatinine, uric acid, ALT, AST,
 26 LDH, CPK, Alkaline Phosphatase, total and direct bilirubin, albumin, total protein), CBC
 27 (hematocrit, hemoglobin, white blood cell count and differential, platelet count).
 28 Testing will also be done for anti-HAV, HBsAg, anti-HBs, HBeAg, anti-HBe, anti-HBc,
 29 anti-HCV, and stored sample for IL-28b testing. Baseline HBV DNA level by quantitative
 30 PCR (COBAS Ampliprep/COBAS Taqman HBV v2.0 Test: Roche Diagnostics, lower limit
 31 of quantification 116 copies /ml or 20 IU/ml, lower limit of detection 6 IU/ml)
- 32 (7) Extended blood panel: alpha fetoprotein, gGT, immunoglobulins, rheumatoid factor,
 33 ANUCs, SMA, lipid panel, thyroid panel, INR, reticulocyte count, ESR.
 34

- 1 (8) Research blood- one 10 ml serum and one 10 ml plasma tube stored frozen in 0.5-1.0
2 mL aliquots). The stored serum and plasma will be used to measure selected cytokines,
3 interferon-stimulated gene products [including IP10], quantitative HBsAg level (by
4 using the Roche Elecsys HBsAg automated quant assay) and for future research.
- 5 (9) Fifty milliliters of whole blood (green top tubes) for baseline immunological studies: NK
6 cell responses, CD4+ and CD8+ T cell HBV specific responses (peripheral blood
7 mononuclear cell [PBMC] studies)
- 8 (10) Urine tests: routine urinalysis and a pregnancy test for females of childbearing
9 potential
- 10 (11) Transient elastography
- 11

12 **Admission for pretreatment liver biopsy**

13

14 Once patients are deemed eligible to participate in the study based on results of the screening
15 labs, they will have 12 weeks to complete the liver biopsy and to begin add-on therapy with
16 peginterferon. Eligible patients will be admitted to 5NW to undergo a percutaneous liver biopsy.
17 The initial liver biopsy will be mostly for research purposes to measuring baseline levels of ISG
18 expression, pregenomic and cccDNA concentration and frequency and activity of liver infiltrating
19 HBV-specific NK cells but will also be used for the purpose of grading and staging of liver disease
20 before treatment and will provide useful information to the clinician and patient on whether the
21 liver disease is improving on current therapy. Grading and staging of the liver biopsy will

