23 peginterferon-alpha 2a (PEGASYS®, Roche), 180 mcg per week administered by subcutaneous
24 injection for a total of 24 weeks. Patients will continue treatment with their previous nucleosi(t)ide
25 analogue regimen during the treatment and follow-up phases of this study.

26 Patients will be seen in the outpatient clinic at weeks 2, 4, 8, 12, and 24, during treatment phase, at
27 12 week intervals thereafter up to 48 weeks post-therapy

28 Compliance will be monitored by medication diaries and counting of the residual vials returned at
29 outpatient visits. The side effects will be monitored regularly at each visit during the treatment phase
30 of the study by symptom questionnaires. Peginterferon alfa-2a will be dose reduced or stopped per
31 the dose reduction and stopping rules for peginterferon alfa-2a. Peginterferon alfa-2a treatment can
32 be restarted if the adverse event resolves and the patient is willing to re-start the medication.

33

34 **On-treatment liver biopsy**

35

1 At day 0, all patients will be readmitted to the NIH Clinical Center to start therapy with peginterferon
2 alfa-2a and to undergo a repeat liver biopsy. Biopsy will be scheduled at 6 hours following the first
3 injection of peginterferon, for the purpose of assessing ISG response pattern following the initial
4 exposure to peginterferon. Liver tissue will also be subjected to routine histopathological grading
5 and staging as well as for immune cell, quantitative viral kinetic and cccDNA epigenetic studies as
6 previously described.

7
8 Since the hypothesis to be tested in this study is that response to treatment peginterferon (i.e. loss of
9 HBeAg and HBsAg or both) is mediated by changes in hepatocyte gene transcription profile, it is
10 necessary to obtain liver tissue at two time points-before and 6 hours after the first dose of
11 interferon. Performing two liver biopsies within 12 weeks or even as short as 24 hours has been
12 performed in other Liver Disease Branch studies and has not been associated with an increase in the
13 complication rate or lower patient acceptance.

16 **Monitoring**

17 Day 0

- 18
- 19
- 20 1) Brief clinical evaluation
- 21 2) Review patient's eligibility for study
- 22 3) Symptom questionnaire
- 23 4) Visual analogue scale
- 24 5) Fatigue questionnaire (Promise 7)
- 25 6) Chemistry 20 (sodium, chloride, potassium, bicarbonate, calcium, phosphate, magnesium,

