26 glucose, blood urine nitrogen, creatinine, uric acid, ALT, AST, LDH, CPK, Alkaline
27 Phosphatase, total and direct bilirubin, albumin, total protein), CBC (hematocrit, hemoglobin,
28 white blood cell count and differential, platelet count).
- 29 7) Females of child bearing potential: Pregnancy test
- 30 8) HBV DNA , qualitative and quantitative HBeAg, HBsAg, measurements
- 31 9) 30 mL of blood in heparinized green top tubes for NK and T cell analysis prior to PegIFN
32 injection and 30 mL of blood in heparinized green top tubes for NK and T cell analysis 6h
33 after PegIFN injection.
- 34 10) Blood sample for storage (10 mL of blood separated into serum and stored frozen in 0.5-1.0
35 mL aliquots)
- 36 11) Start peginterferon 180 ug SQ

1 12) Repeat liver biopsy 6 hours after first dose of peginterferon. Liver biopsy cut into four
 2 sections, one (at least 1.5 cm) placed in formalin for routine light microscopy and the other 3
 3 (.3cm, .5cm and 1 cm) placed in RNAlater and flash frozen in liquid nitrogen 24 hours later
 4 for RNA and protein analyses and flow cytometry.

5
 6
 7

8 Day1

9 1) 24h after the first PegIFN injection: 50 mL of blood in heparinized green top tubes for NK.
 10 This is the time point where we expect the maximal response of NK cells to PegIFN based on
 11 our previous studies [35, 36]
 12 2) Discharge from hospital

13

14

15 **Week 2,4, 8 and 12 (\pm 3 days):** Outpatient visit

16 Each outpatient visit will include assessment of compliance, adverse events reporting, vital signs,
 17 weight, symptoms evaluation, record of concomitant medications, drug dispensing

- 18 1) Symptom questionnaire
- 19 2) Visual analogue scale
- 20 3) Fatigue questionnaire (Promise 7) (week 2 only)
- 21 4) Chemistry 20 (sodium, chloride, potassium, bicarbonate, calcium, phosphate, magnesium,
 22 glucose, blood urine nitrogen, creatinine, uric acid, ALT, AST, LDH, CPK, Alkaline
 23 Phosphatase, total and direct bilirubin, albumin, total protein), CBC (hematocrit, hemoglobin,
 24 white blood cell count and differential, platelet count).
- 25 5) HBV DNA viral load, HBeAg, anti HBe, HBsAg and anti HBs measurment
- 26 6) Blood sample for storage (10 mL of blood separated into serum and plasma stored frozen in
 27 0.5-1.0 mL aliquots)
- 28 7) 50 mL of blood in heparinized green top tubes for NK and T cell analysis.
- 29 8) Females of child bearing potential: Pregnancy test
- 30 9) TSH and quantitative HBe and HBs antigen measurement at week 12.

31

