32

33 **End of Add-on Peginterferon Treatment (Week 24 \pm 3 days)**

34 At week 24, all subjects will discontinue peginterferon alfa-2a add-on therapy (but continue the
 35 NUCs and undergo the following evaluation:

- 1 1) Physical examination
- 2 2) Symptom questionnaire
- 3 3) Fatigue questionnaire (Promise 7)
- 4 4) Visual analogue scale
- 5 5) Assessment of adverse events, concomitant medications and adherence
- 6 6) Blood will be drawn for Chemistry 20 (sodium, chloride, potassium, bicarbonate, calcium,
- 7 phosphate, magnesium, glucose, blood urine nitrogen, creatinine, uric acid, ALT, AST, LDH,
- 8 CPK, Alkaline Phosphatase, total and direct bilirubin, albumin, total protein), CBC
- 9 (hematocrit, hemoglobin, white blood cell count and differential, platelet count).
- 10 7) 50 mL of blood in heparinized green top tubes for NK and T cell analysis.
- 11 8) Urine tests: routine urinalysis and creatinine, phosphate and beta-2-microglobulin
- 12 9) HBV DNA viral load, HBeAg, anti-HBe, HBsAg, anti-HBs and quantitative HBe and HBs
- 13 measurement
- 14 10) Blood sample for storage (10 mL of blood separated into serum and plasma stored frozen in
- 15 0.5-1.0 mL aliquots)
- 16 11) Females of child bearing potential: Pregnancy test
- 17 12) TSH

18

19 **Post-treatment weeks 12, 24, 36 (\pm 5 days)**

- 20 1) Limited clinical evaluation
- 21 2) Symptom questionnaire
- 22 3) Visual analogue scale
- 23 4) Routine blood panel: Chemistry 20 (sodium, chloride, potassium, bicarbonate, calcium,
- 24 phosphate, magnesium, glucose, blood urine nitrogen, creatinine, uric acid, ALT, AST, LDH,
- 25 CPK, Alkaline Phosphatase, total and direct bilirubin, albumin, total protein), CBC
- 26 (hematocrit, hemoglobin, white blood cell count and differential, platelet count).
- 27 5) HBV DNA viral load, HBeAg, anti HBe, HBsAg and anti HBs levels
- 28 6) Blood sample for storage (10 mL of serum and 10 ml of plasma stored frozen in 0.5-1.0 mL
- 29 aliquots)
- 30 7) 50 mL of blood in heparinized green top tubes for NK and T cell analysis.

31

32

33 **Final study visit week 48 post-treatment (\pm 5 days)**

- 34 1) Limited clinical evaluation
- 35 2) Symptom questionnaire

- 1 3) Fatigue questionnaire (Promise 7)
 2 4) Visual analogue scale
 3 5) Routine blood panel: Chemistry 20 (sodium, chloride, potassium, bicarbonate, calcium,
 4 phosphate, magnesium, glucose, blood urine nitrogen, creatinine, uric acid, ALT, AST, LDH,

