 5 CPK, Alkaline Phosphatase, total and direct bilirubin, albumin, total protein), CBC
 6 (hematocrit, hemoglobin, white blood cell count and differential, platelet count).
 7 6) Extended blood panel: alpha fetoprotein, gGT, immunoglobulins, rheumatoid factor, ANA,
 8 SMA, lipid panel, INR, reticulocyte count, ESR.
 9 7) 50 mL of blood in heparinized green top tubes for NK and T cell analysis.
 10 8) HBV DNA viral load, HBeAg, anti HBe, HBsAg, and anti HBs levels and quantitative HBe and
 11 HBs measurement
 12 9) Blood sample for storage (10 mL of serum and 10 ml of plasma stored frozen in 0.5-1.0 mL
 13 aliquots)
 14 10) Fibroscan
 15

16 **Table 1: List of study related procedures**
 17

Procedure	Screen	Pre-Rx biopsy	Day 0	Wk 2, 4, 8	Wk 12	Week 24 End of Rx	Post-Rx wk 12, 24, 36	Post-Rx wk 48, End of Study
H&P/breif clinical evaluation, compliance, AE, concomit. drugs, etc	X	X	X	X	X	X	X	X
Symptom questionnaire	X	X	X	X	X	X	X	X
Visual Analog Scale	X	X	X	X	X	X	X	X
Promis 7	X	X	X	wk 2		X		X
Chem 20	X	X	X	X	X	X	X	X
CBC	X	X	X	X	X	X	X	X
Anti-HAV	X							
HBsAg	X	X	X	X	X	X	X	X
HBsAg quantitative			X		X	X		X
anti-HBs	X							
HBeAg	X	X	X	X	X	X	X	X
HBeAg quantitative			X		X	X		X
anti-HBe	X							
anti-HBc	X							

anti-HCV	X							
IL28B	X							
HBV DNA	X	X	X	X	X	X	X	X
AFP	X							X
gGT	X							X
Immunoglobulins	X							X
rheumatoid factor	X							X
ANA	X							X
SMA	X							X
Lipid panel	X							X
thyroid panel	X				TSH	TSH		
INR	X							X
reticulocyte	X							X
ESR	X							X
storage - 5mL serum and 5mL plasma	S&P	Serum	Serum	S&P	S&P	S&P	S&P	S&P
Immunology - 50mL	X	X	X	X	X	X		X
Urine pregnancy	X		X	X	X	X		
UA	X					X		
Urine creatinine, phosphate, beta-2-microglobulin						X		
Liver Biopsy		X	Time d					
Abdominal u/s		X						
CXR		X						
EKG		X						
Fibroscan	X							X

1

2

3

4

5

ASSESSMENT OF RESPONSE

6

Clinical Definitions

7

8

a) **Loss of HBeAg (HBeAg-positive patients only):** loss of detectable HBeAg with or without anti-HBe seroconversion confirmed on 2 consecutive visits at least 12 weeks apart.

9

10

b) **Loss of HBsAg:** Loss of HBsAg, with or without anti HBs seroconversion confirmed on 2 consecutive visits at least 12 weeks apart.

11

- 1 c) **Sustained response:** virological, serological, biochemical, or combined response present at
2 the time of last observation and at least six months after stopping therapy.

3

4

5 The primary goals of this study are centered on understanding the mechanisms, and identification of

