16 major risk to subjects who agree to participate in this study is the risk of undergoing 2 liver biopsies
17 (as outlined in Risks and hazards #3). Since a major endpoint of the study is to understand how
18 peginterferon may lead to HBeAg or HBsAg loss, the timing of the biopsies were chosen to maximize
19 our ability to demonstrate changes in interferon stimulated genes in the liver-up to 12 weeks before
20 and 6 hours after the first dose of peginterferon. Knowledge gained from this analysis may inform on
21 how best to use peginterferon in patients with chronic hepatitis B and identify new approaches to
22 induce HBeAg and HBsAg loss-highly desirable endpoints that may permit cessation of treatment.
23

24 **Potential benefits**

25 For patients with chronic hepatitis B, the strategy of add-on peginterferon offers a potential benefit
26 of loss of either HBeAg or HBsAg or both with the possibility of discontinuing all therapy and removal
27 of the risks associated with long term nucleoside analogue use-predominantly renal toxicity and
28 bone loss with tenofovir and cancer risk with entecavir. Thus, there is a prospect of overall clinical
29 benefit from participation in this study.
30

31 **DATA AND SAFETY MONITORING**

32

33 The adequacy of data acquisition and storage of samples and the monitoring of safety in this trial will
34 be performed by the principal investigator in collaboration with the associate investigators. Data and
35 safety are reviewed weekly in clinical research rounds by the Liver Diseases Branch, NIDDK. These
36 rounds are separate from regular clinical rounds and consist of review of all study patients including

1 flow sheets of major safety and efficacy measurements without knowledge of which therapy is used.
2 Monitoring of this study will also be conducted by the statistical department of NIDDK who will have
3 knowledge of the patient allocation. Reports of serious adverse events are made to the Clinical
4 Director NIDDK, and the IRB as outlined below.
5

6 **ADVERSE EVENT REPORTING**

7 **Definitions**

9

10 Protocol Deviation: Any change, divergence, or departure from the IRB approved research protocol.

11 Unanticipated Problem: Any incident, experience or outcome that meets all of the following criteria:

12 1. Unexpected (in terms of nature, severity or frequency) given (a) the research procedures
13 that are described in the protocol-related documents, such as the IRB approved research protocol

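### Urine creatinine, phosphate and beta-2-microglobulin are scheduled only at week 24, so change in these three markers cannot be derived for any patient

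*Combined protocol and SAP*

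**What the plan says.** The week 24 list (End of Add-on Peginterferon Treatment, item 8) orders "Urine tests: routine urinalysis and creatinine, phosphate and beta-2-microglobulin". In Table 1 the row "Urine creatinine, phosphate, beta-2-microglobulin" has a single mark, under Week 24 End of Rx.

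Before the first dose, Screening item 10 has "Urine tests: routine urinalysis and a pregnancy test for females of childbearing" potential. The pre-treatment biopsy admission lists no urine test. On day 0 the only one is for a subset: "Females of child bearing potential: Pregnancy test". The storage provisions cover serum, plasma and liver tissue, not urine.

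Three other parts of the protocol bear on the point:

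- The end-point paragraph of the Background includes, among other secondary end-points, changes "in quantitative HBeAg and HBsAg levels during therapy and safety of the combination regimen".
- Potential benefits speaks of removal "of the risks associated with long term nucleoside analogue use-predominantly renal toxicity and" bone loss. The Hazards section says that interferon may have minor renal toxicity.
- Exclusion criterion 11 removes patients with "eGFR < 50 ml/min, serum creatinine > 1.3 mg/dl or urine protein >1 gram/24-hours".

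**The concern.** A safety marker measured once, at the end of treatment, shows a level and not a change. Every patient enters after at least 192 weeks of NUCs (192/52 = about 3.7 years) and continues them during the study, and there is no concurrent control. A raised beta-2-microglobulin or abnormal phosphate excretion at week 24 might have been there before the first injection. A normal value might hide a rise within the normal range. The sponsor would pay for up to 60 sets of assays and could not say whether any abnormality was new on the combination, although safety of the combination is a stated interest of the study.

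**Working it through.** The plan gives no figure to reproduce on this point. The check compares each visit list with Table 1 and counts scheduled values per patient.

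| Visit | Three urine markers | Routine urinalysis | Serum chemistry (Chem 20) |
|---|---|---|---|
| Screening | no | yes | yes |
| Pre-treatment biopsy | no | no | yes |
| Day 0 | no | no | yes |
| Weeks 2, 4, 8 | no | no | yes |
| Week 12 | no | no | yes |
| Week 24 | yes | yes | yes |
| Post-treatment weeks 12, 24, 36 | no | no | yes |
| Post-treatment week 48 | no | no | yes |

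The visit lists and the table agree, so this is neither an internal conflict nor a table damaged in conversion.

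**Count for the three markers.** Scheduled values per patient are 0 before peginterferon, 1 at week 24 and 0 afterwards. Baseline-to-week-24 pairs per patient = min(0, 1) = 0, and 60 × 0 = 0 for the study. With one pre-dose collection, pairs per patient = min(1, 1) = 1, so at most 60 × 1 = 60, fewer with drop-out.

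**Indices that need these markers.**

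- Beta-2-microglobulin/creatinine ratio = urine beta-2-microglobulin ÷ urine creatinine. Both inputs exist at week 24 and neither exists before the first dose.
- Fractional phosphate excretion = (urine phosphate × serum creatinine) ÷ (serum phosphate × urine creatinine). At week 24 all four inputs exist. At screening and day 0 the two serum inputs exist and the two urine inputs do not.

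**Comparison with the rest of the schedule.** Every other Table 1 row with a value after dosing starts also has one before the first dose or, for the biopsy, a pre-treatment sample. Quantitative HBsAg and HBeAg have day 0. The thyroid panel, urinalysis, AFP, INR and Fibroscan have screening. This row is the only exception, which suggests an oversight more than a choice.

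**What remains measurable.** Chem 20, listed as "Chemistry 20 (sodium, chloride, potassium, bicarbonate, calcium, phosphate, magnesium" and further analytes, includes serum creatinine, phosphate, potassium, bicarbonate and uric acid. It is marked in all eight visit columns. Routine urinalysis gives one screening-to-week-24 pair.

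**The case against.** The strongest reply is that renal safety is already monitored. Serum chemistry is serial from screening to the final visit, urinalysis is paired, and criterion 11 excludes substantial renal impairment at entry. A reader might infer from the single urine time point that renal tubular change cannot be examined at all. The documents do not support that, because the serum and urinalysis data allow an indirect look. They are less specific for tubular function, however, and criterion 11 records no baseline value of the three markers.

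Second, the markers feed no listed result. The formal primary and secondary endpoint lists contain no safety or renal item, the statistical section plans no renal analysis, and the renal rows of Table 2 use only creatinine clearance and hemodialysis. This stands and limits the weight of the point. The Background also says that safety will be compared with historical controls, but it does not say that those trials measured these markers, and published rates cannot supply a patient's own baseline.

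Third, the renal risk may be narrower and smaller than it sounds. The Potential benefits sentence goes on to name tenofovir, and the share of patients on tenofovir is not given. The Background does attach renal toxicity to long-term NUC therapy in general. The Hazards section puts renal complications of interferon below 1%, which is fewer than 0.01 × 60 = 0.6 patients, but that rate concerns clinical complications and not subclinical marker changes. No prevalence of abnormal markers after long NUC use is given, so the number of patients likely to be misread cannot be estimated.

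Finally, a reader might infer that a baseline would let the sponsor attribute a renal change to peginterferon. It would not. NUCs continue alongside peginterferon and there is no control arm, so a within-patient change mixes the two.

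**Conclusion.** The point holds for these three urine markers. As scheduled, change is derivable in 0 of 60 patients, and an abnormal week 24 value cannot be separated from one that predates peginterferon. With no post-treatment value, persistence or reversal cannot be seen either. Nothing in the primary or listed secondary endpoints changes, and crude renal monitoring remains. This is a low-cost improvement to the safety data, not a flaw in the main analysis.

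The conclusion assumes that the schedule is followed as written and that no earlier urine values are used. Patients recruited from the two existing protocols might have such values, but the documents neither say so nor plan to use them.

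**What to change.** Add urine creatinine, phosphate and beta-2-microglobulin to Screening item 10 and mark the Screen column in that row of Table 1. Alternatively, add them to a pre-dose urine at day 0 and mark that column. Day 0 is nearer the first dose: up to 12 weeks may pass between confirmed eligibility and the start of peginterferon, so a screening-to-week-24 interval could span about 12 + 24 = 36 weeks. But day 0 urine is planned only for women of childbearing potential, so using day 0 for everyone would need one extra urine collection in the others.

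State a descriptive safety read-out: week 24 minus baseline change in the beta-2-microglobulin/creatinine ratio and in fractional phosphate excretion, using the serum creatinine and phosphate already drawn. Say in the plan that this identifies abnormalities new on the combination and does not separate peginterferon from continued NUC use.

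The cost is up to about 60 extra assay sets. The screening option needs no new visit or procedure. The sample must be taken before the first dose, because no stored urine would allow the baseline to be recovered later.
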